6.1.3. Immunogenicity Visit Windows

For immunogenicity summaries and tabulations per time point, assessments will be allocated to an analysis visit based on the planned visit as captured in the CRF. Visits that are out of the protocol-defined visit windows (see table below) will not be included in the immunogenicity summaries and tabulations per timepoint. However, they may be included in sensitivity analyses.

Table 6: Immunogenicity timepoints

Analysis timepoint	Reference day	Target day (counted from the reference day)	Window
Baseline	Day of vaccination	1	(-inf, 1]
Day 15	Day of vaccination	15	[15, 18]
Day 85	Day of vaccination	85	[78, 92]
Day 169	Day of vaccination	169	[155, 183]
Day 365/Month 12	Day of vaccination	365	[358, 379]
Day 533	Day of vaccination	533	[519, 547]

Immunogenicity samples taken during an ARI will be allocated to an analysis timepoint based on the relative day during the ARI and the below windowing. The relative day during the ARI is determined as ARI visit date – ARI start date +1. ARI immunogenicity timepoints will only be part of the correlate of protection analysis and predictive immune marker assessment where possible. Immunogenicity analysis related to correlate of protection will be described in a separate SAP.

Table 7: Immunogenicity timepoints during an ARI

Analysis timepoint	Reference day	Target day (counted from the reference day)	Window
ARI Day 3-5	Start date of ARI	4	[1,7]

6.2. Participant Dispositions

Participant information will be shown for the full analysis set, safety subset, PPE, PPI as well based on the risk level of the participant.

The number of participants in the following disposition categories will be summarized throughout the study by intervention group and overall:

- participants screened
- participants in the FAS
- participants in the PPI
- participants in the PPE
- participants vaccinated and not randomized
- participants randomized and not vaccinated
- participants not randomized and not vaccinated
- participants randomized and vaccinated
- participants who discontinued study
- participants who discontinued vaccination (for participants that discontinued before amendment 4 was approved)
- reasons for termination (with special interest on the COVID-19 related reasons)

Also, the number of participants and percentage per phase will be tabulated.

The time that participants are followed in the study will be summarized descriptively, for the FAS and PPE. The time that participants are followed in the study based on the FAS is defined as time between vaccination and the minimum between study completion, discontinuation or database cut off and based on the PPE is defined as time between vaccination and the minimum between study completion, discontinuation or database cut off or Day 365 planned visit (or relative day 365 if no planned Day 365 is present but there are ARI surveillance questions available after the relative day

365), in case the participant had a major protocol deviation impacting efficacy during the second year.

6.3. Primary Endpoint Analysis

The primary endpoint of the study is the first occurrence of RT-PCR-confirmed RSV-mediated LRTD, with onset at least 14 days after dosing with study vaccine.

The PPE will be used to analyze the primary efficacy endpoint.

6.3.1. Definition of Endpoint

A participant will be considered to have RT-PCR-confirmed RSV-mediated LRTD if the following criteria are met:

- New onset or worsening from baseline of 3 or more of the below symptoms as captured in the RiiQ at the same assessment time point:
 - Cough
 - Short of breath
 - Coughing up phlegm (sputum)
 - Wheezing
- AND
- Confirmation of RSV by RT-PCR in one or more of the nasal swabs, or in the sputum sample (when available)

Prior to database lock for all planned analyses, the CEC will review all available data of all RT-PCR confirmed RSV-mediated ARIs and will confirm if the above criteria are met. If the CEC confirms that the criteria for RT-PCR-confirmed RSV-mediated LRTD are met, the cases will be counted as a primary endpoint in the statistical analysis. This will be done in two steps:

Step 1:

The set of RT-PCR confirmed RSV-mediated ARIs for which the CEC will review all available data will be determined programmatically as follows:

ARI episode definition

An ARI episode is defined as an episode reported by the participant and confirmed by the site, which is captured on the ‘Acute Respiratory Infection’ form of the CRF, meaning that all ARIs with a confirmed start (CESTDTC) and end (CEENDTC) date on this form will be considered an ARI episode. ARIs initiated by error and their respective symptoms will be removed from the analysis.

Note: In the cases that an RSV ARI is ongoing during the DB cut off, the database cutoff date will be used as an interim ARI end date for the purposes of the analysis. An ARI with no end date will be considered as an RSV ARI, if an RSV positive result is available within 15 days after the ARI onset.

ARI episode duration

The duration of an ARI episode is defined based on the ARI start and ARI end date reported in the CRF: *end date of ARI - start date of ARI + 1 (CEENDTC - CESTDTC + 1)*.

RSV RT-PCR Confirmation of the Considered ARI Episode

Confirmation of RSV infection by RT-PCR for the primary endpoint will be done in nasal swabs or sputum samples.

For samples collected outside of China, a sample is considered RSV positive if:

- Confirmation of RSV infection by RT-PCR in nasal swabs is obtained at the site laboratory with the BioFire Filmarray RP2.1-EZ panel, which will be provided to all sites (both US and non-US, except China sites). Both the home swab and the site swab will be analyzed at the site. The confirmation of RSV infection from the nasal swab at central laboratory using BioFire will not be taken into account for the primary endpoint, unless in the unlikely event where at least one nasal swab from an ARI episode cannot be tested at the site (eg, in the setting of instrument malfunction or shortage of testing reagents at the site).
- Confirmation of RSV infection by RT-PCR in sputum samples (when collected) is obtained in the central laboratory with the Biofire Filmarray PN panel.
- For participants hospitalized with symptoms of an ARI, confirmation of RSV infection using a locally approved RT-PCR test obtained at the hospital laboratory can also be used. These results will be used in the primary analysis only if approved by an independent expert with expertise in diagnostic testing. The approval of the RT-PCR results by the expert will be based on the specifications of the test performed, the qualifications of the testing laboratory and the procedures followed in the laboratory.

For samples collected in China, a sample is considered RSV positive if:

- Confirmation of RSV infection by RT-PCR in nasal swabs is obtained at the site laboratory with the Cepheid GeneXpert Flu-RSV XPRESS, which will be provided to all China sites. Both the home swab and the site swab will be analyzed at the site. The confirmation of RSV infection from the nasal swab at central laboratory using Cepheid GeneXpert Flu-RSV XPRESS will not be taken into account for the primary endpoint, unless in the unlikely event where at least one nasal swab from an ARI episode cannot be tested at the site (eg, in the setting of instrument malfunction or shortage of testing reagents at the site).
- Confirmation of RSV infection by RT-PCR in sputum samples (when collected) is obtained in the central laboratory with the Biofire Filmarray PN panel.
- For participants hospitalized with symptoms of an ARI, confirmation of RSV infection using a locally approved RT-PCR test obtained at the hospital laboratory can also be used. These results will be used in the primary analysis only if approved by an independent expert with expertise in diagnostic testing. The approval of the RT-PCR results by the expert will

be based on the specifications of the test performed, the qualifications of the testing laboratory and the procedures followed in the laboratory.

One positive sample (defined as any sample with a value above the limit of detection) is sufficient.

Any nasal swab and/or sputum sample taken within 7 days after start of an ARI episode or during the ARI episode will be allocated to that ARI. In case of 2 consecutive ARI episodes, where the second ARI starts within 7 days after the onset of the first episode and the ARI Day 3-5 sample of the first episode is taken while the second episode is ongoing, then the nasal swab and/or the sputum sample will be attributed to both ARIs.

Step 2:

For the set of RT-PCR confirmed RSV-mediated ARIs, the CEC will determine if the protocol defined criteria for LRTD (as specified in the beginning of this section) are met, using the following framework.

Counting of symptoms during an ARI episode to determine if LRTD criteria are met

To meet the primary endpoint, new onset or worsening from baseline in 3 or more LRTD symptoms (cough, short of breath, coughing up phlegm, wheezing) collected at the same assessment timepoint are required.

Symptoms present during an ARI episode but not at the baseline assessment will be considered as symptoms with a new onset. Symptoms present at the baseline assessment that become worse (higher severity) during the ARI episode will be considered as worsening symptoms. Missing baseline assessments will not be imputed, in case of missing baseline symptoms the participant will be considered to have no baseline symptoms at all. The baseline is defined in Section 6.1.1. Only assessments occurring during the ARI episode as defined above will be taken into account. Any assessment collected outside this period will not be used for counting symptoms.

Counting of the number of symptoms with new onset or worsening will be done per assessment timepoint. If a participant completed the RiiQ more than once per day, the case definitions cannot be met by combining symptoms from different assessments on that day, the required number of symptoms must be attained at one assessment.

Note: Only symptoms collected between the start of the ARI (CESTDTC) and the end of the ARI (CEENDTC) will be used for determining if the LRTD criteria are met.

Examples:

If a participant had an ARI lasting 4 days, with the following new onset or worsening of symptoms compared to baseline:

ARI Day 1: new onset of cough

ARI Day 2: new onset of wheezing and worsening of short of breath

ARI Day 3: new onset of cough and wheezing

ARI Day 4: worsening of short of breath

This participant does not meet the conditions of an LRTD.

If another participant had an ARI lasting 5 days, with the following new onset or worsening of symptoms compared to baseline:

ARI Day 1: new onset of cough

ARI Day 2: new onset of wheezing and worsening of short of breath and new onset of cough

ARI Day 3: new onset of cough and wheezing

ARI Day 4: new onset of cough

ARI Day 5: new onset of cough

This participant meets the condition of an LRTD at ARI Day 2.

Finally, if a participant completed by accident two RiiQ assessments at the same day, but at different timepoints with the following symptoms:

ARI Day 1: new onset of cough

ARI Day 2 (1st assessment): new onset of wheezing and worsening of short of breath

ARI Day 2 (2nd assessment): new onset of cough

ARI Day 3: new onset of cough and wheezing

ARI Day 4: new onset of cough

ARI Day 5: new onset of cough

This participant does not meet the conditions of an LRTD, since symptoms of two assessments cannot be combined.

RT-PCR confirmed RSV-mediated ARIs confirmed by the CEC as RSV-mediated LRTDs will be counted as primary endpoint in the statistical analysis, as per table below.

Table 8: Adjudicator's choices and selection for the primary endpoint

Option in the Adjudication System	Option in the Database	Included as Primary Endpoint
RSV positive ARI meets the CTP-defined criteria for RT-PCR confirmed RSV-mediated LRTD (in accordance with the programmed case definition)	RSV MEDIATED LRTD BOTH PROGRAMMED AND BY CEC	Yes
RSV positive ARI meets the CTP-defined criteria for RT-PCR confirmed RSV-mediated LRTD, but not classified as RT-PCR confirmed RSV-mediated LRTD by the medical assessment of CEC	RSV MEDIATED LRTD PROGRAMMED BUT NOT BY CEC	No
RSV positive ARI does not meet CTP-defined criteria for RT-PCR confirmed RSV-mediated LRTD but classified as RT-PCR confirmed RSV-mediated LRTD by the medical assessment of CEC	RSV MEDIATED LRTD BY CEC BUT NOT PROGRAMMED	Yes
RSV positive ARI not meeting CTP-defined criteria for RT-PCR confirmed RSV-mediated LRTD nor is classified as RT-PCR confirmed RSV-mediated LRTD by the medical assessment of CEC	NO RSV MEDIATED LRTD	No

For the analyses, unless explicitly specified, ‘RSV-mediated LRTDs’ is always referring to the ones assessed as such by the CEC.

6.3.2. Level of Significance

The total alpha will be controlled at 2.5%. A Pocock-like alpha spending function as described by DeMets (DeMets 1994) with a target number of events of 76 will be used to spend the alpha over the different analyses. The different alphas to be used during every IA are shown in [Figure 1](#) and the calculations are explained below in [Table 9](#)

Table 9: Alpha spending at the Prespecified Analysis Timepoints

Alpha	Description of how to obtain alpha
α_1	Alpha obtained from Pocock-like alpha spending function with information fractions = [# RSV LRTD events by 15 September 2022 / 76 [¥] , 1]
α_2	Alpha obtained from Pocock-like alpha spending function with information fractions = [# RSV LRTD events by 15 September 2022 / 76 [¥] , # RSV LRTD events by 24 October 2022 / 76 [¥] , 1]
α_3	Alpha obtained from Pocock-like alpha spending function with information fractions = [# RSV LRTD events by 15 September 2022 / 76 [¥] , # RSV LRTD events by 24 October 2022 / 76 [¥] , # RSV LRTD events by 22 Jan 2023 / 76 [¥] , 1]
α_4	Alpha obtained from the remaining alpha to be spent (2.5% - total alpha spent during the interim analyses) and the actual information fractions observed at all analyses. That is, the information fraction, IF = [# RSV LRTD events by 15 September 2022 / # RSV LRTD events by 30 April 2023, # RSV LRTD events by 24 October 2022 / # RSV LRTD events by 30 April 2023, # RSV LRTD events by 22 January 2023 / # RSV LRTD events by 30 April 2023, 1]. The final alpha will be calculated using the user-defined alpha spending function approach (Jennison 2000).

More details related to the significance level the secondary efficacy endpoints will be tested can be found in Section [6.4.1.2](#). Refer to Section [2](#) for more details on the success criterion.

6.3.3. Analysis Methods

The analysis of the primary endpoint will evaluate the first occurrence of RT-PCR-confirmed RSV-mediated LRTD with onset of at least 14 days after the vaccination in the active vaccine group compared to the placebo group in the PPE population. Time at risk will also be taken into account. The null hypothesis of LL \leq 20% for RT-PCR-confirmed RSV-mediated LRTD will be tested versus the alternative hypothesis of LL $>$ 20%. Additionally, the observed VE should be $>$ 50%.

Model:

Exact Poisson regression will be fitted with the event rate, defined as the number of events (with onset at least 14 days after vaccination) over the follow-up time (off-set) as dependent variable and the vaccination group, being at increased risk of RSV disease and age strata (both variables as stratified) as independent variables.

The model is defined with the *proc genmod* function in SAS, with an *offset* statement and a *log* (natural logarithm) link. The *exact* statement with the *estimate = both* option and an *alpha = 2**

significance level from Section 6.3.2 is used to calculate the relative risk ratio and its confidence interval. The Vaccine Efficacy is then calculated as $1 - \text{Relative Risk Rate}$.

In case the algorithm does not converge, age and risk level will be removed from the model.

Each participant will be taken into account in the model with one observation indicating whether they had an event or not, the vaccination group, the stratification factors and the follow up time.

Follow up time:

The follow-up time is defined as the time between 14 days post vaccination (vaccination day + 14 days) and occurrence of the first event; for participants with no events, it is the time between 14 days post vaccination and the minimum of the database cut-off date of the analysis. However, for participants who discontinued or completed the study before having an event, follow-up time is defined as the time between 14 days post vaccination and the date of last contact (day of discontinuation or completion).

For participants with an MPD impacting efficacy during the second year (during the second year follow up period), only the first year data are taken into account: for cases during the first year, the follow - up time is defined as the time between 14 days post-vaccination and occurrence of the first event . For non-cases, it is the time between 14 days post - vaccination and the day before Day 365 visit (or relative day 365, in case Day 365 not available but there are ARI surveillance questions available after the relative day 365). Thus, all participants will be included in the analysis according to their follow-up time.

Note: Occurrence is always referring to the start of the ARI as reported in the CRF (CESTDTC).

As **sensitivity analyses** the above Poisson model will be repeated similar to the primary analysis:

- based on the FAS (which also does not take into account the restriction on the onset [at least 14 days] and will count follow up from vaccination on Day 1 onwards).
- based on the PPE set but excluding coinfections with other respiratory viruses, based on the Biofire - Filmarray assay (Section 7.7) or the Cepheid GeneXpert (for swabs in China sites). This should be detected in one of the scheduled nasal or sputum samples linked to the respective ARI but should not necessarily be detected in the same sample as the one that resulted in RSV confirmation.
- based on the PPE set but excluding coinfections with other respiratory viruses or bacteria, based on the Biofire - Filmarray assay (Section 7.7) or the Cepheid GeneXpert (for swabs in China sites). This should be detected in one of the scheduled nasal or sputum samples linked to the respective ARI but should not necessarily be detected in the same sample as the one that resulted in RSV confirmation.
- based on the PPE set with age and increased risk status as collected (instead of as stratified) in case there are many discrepancies between as collected and as stratified.

- based on the PPE set but excluding RSV positive tests from local hospital assays of hospitalized participants.
 - based on the PPE set, using the only central RSV results by Biofire Filmarray PN panel, Cepheid GeneXpert and BioFire Filmarray RP2.1-EZ and the approved local RT-PCR test from hospitalization cases. This sensitivity analysis will only be performed, if there are positive RSV cases based on the local site results of the Cepheid GeneXpert (China sites) or BioFire Filmarray RP2.1-EZ (other sites), that are negative based on the central confirmation.
 - based on the PPE, using a robust Poisson regression similarly defined as the primary endpoint including the minimization factors region (North America, Europe and Southern Hemisphere if applicable), subset (safety, immuno, both or neither) as additional covariates. The model will be fitted in SAS similarly to the primary analysis with a *repeated* statement instead of an *exact* and *type=unstr*. This model will only be performed if the algorithm converges.
 - based on the programmed case definition of RT-PCR confirmed RSV-mediated LRTD, in case there are discrepancies with the CEC adjudication.
 - an exact binomial test (See Section 7.11), which does not take into account strata or follow-up time, based on the PPE population and the FAS. The VE (=1-relative risk) and the corresponding corrected 2-sided CI based on the exact binomial will be calculated as well.
 - based on the PPE set, but instead of focusing on the first occurrence of RT-PCR confirmed RSV-mediated LRTD, the number of events will be used as dependent variable and the offset will be defined as the time between 14 days post vaccination and the minimum of (the database cut-off date, study discontinuation, study completion). For participants with an MPD impacting efficacy during the second year (during the second year follow up period), only the first year data are taken into account, and the follow up will be defined as the time between 14 days post vaccination and the minimum of (the database cut-off date, Day 365 visit -1 or relative day 365 -1, if Day 365 visit not available but there are ARI surveillance questions available after the relative day 365).
 - A sensitivity analysis using multiple imputations will be performed to evaluate the impact of missing RT-PCR results on the primary endpoint. For ARIs where no RT-PCR result can be linked to the considered ARI episode the RT-PCR result (positive or negative) will be imputed using the period the ARI occurred, the geographic location (Europe, Canada, the RSV census regions for USA sites [West, North East, South, Midwest], Latin America [Brazil and Chile], South Africa, Thailand and Oceania [Australia and New Zealand]), the age, the risk level (CDC definition) of the participants and the severity of the episode (*LRTD or not LRTD*) as parameters in the model. The ARI periods will be defined based on the distribution of the cases observed during the study. Moreover, the geographic location grouping might be adjusted to avoid model fitting issues. Based on the model fit parameters might be dropped.
- If one or more RT-PCR test results are available, no imputation will be performed. Moreover, the primary analysis model already accounts for dropouts, since participants follow up time is taken into consideration.

- A rerandomization test will be performed to assess the impact of the minimization algorithm.

If the primary analysis is performed in 2023 the following sensitivity analyses will also be conducted.

- New case will be defined for the second year using Day 365 as baseline to define new onset or worsening of symptoms. The cases of the first year will be defined using Day 1 as baseline. In case the Day 365 visit not available the Day 1 data will be used as baseline for both years. The same Poisson model as the primary endpoint based on the PPE will be performed.
- An exact Poisson model similar to the primary analysis will be performed including an interaction term between the treatment group and the year variables.

The proportion of participants meeting the primary endpoint and the sensitivity analyses, will also be summarized with the corresponding VE and will be depicted with forest plots. The same alpha as in the primary analysis will be used for calculating the CIs.

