6.11. Discontinuation of the study

On the 29th of March 2023 the EVERGREEN study was permanently terminated. All participants are to be followed up for 6 months post vaccinations for safety collection. ARIs will not be collected after the 29th of March 2023 or followed up.

Due to the early termination of the study, the Sponsor decided not to perform the complete planned analysis as described in the protocol and SAP. The final analysis will contain the following:

- Efficacy analysis for secondary endpoints and for a limited selection of the exploratory endpoints.
- Safety analysis presented only per period (as defined in [Table 4](#)).
- Immunogenicity analysis of all completed assays in the database at the time of the analysis.

Moreover, no local specific cohort analysis will be conducted.

The following efficacy endpoints will be analyzed per year and over the whole study:

- First occurrence of any RT-PCR-confirmed RSV-mediated LRTD and ARI
- First occurrence of any RT-PCR-confirmed RSV-mediated LRTD and ARI by subtype
- First occurrence of any clinically relevant diseases associated with RT-PCR-confirmed RSV-mediated LRTD and ARI
- AUC for participants with any RT-PCR-confirmed RSV-mediated LRTD and ARI
- Viral loads

Note: In the cases that an RSV ARI is ongoing during the time of the discontinuation and does not have an end date, the 29th of March 2023 will be used as an ARI end date. An ARI with no end date will be considered as an RSV ARI, if an RSV positive result is available within 15 days after the ARI onset.

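### The imputation model for missing RT-PCR results leaves out vaccination group, so this sensitivity analysis pulls VE toward zero even when results are missing completely at random

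*SAP*

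**What the plan says.** The purpose is stated in SAP 6.3.3: "A sensitivity analysis using multiple imputations will be performed to evaluate the impact of missing RT-PCR results on the primary endpoint". The rule is: "For ARIs where no RT-PCR result can be linked to the considered ARI episode the RT-PCR result (positive or negative) will be imputed". Only episodes with no result at all are affected: "If one or more RT-PCR test results are available, no imputation will be performed".

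The predictors form a closed list. The result is "imputed using the period the ARI occurred, the geographic location", and the list continues with "the age, the risk level (CDC definition) of the participants and the severity of the episode", severity being LRTD or not LRTD. Two adjustments are allowed. Locations may be regrouped, and "Based on the model fit parameters might be dropped". Nothing allows vaccination group to be added, and nothing says imputation is done within arm.

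The exact Poisson model in the same section, which the sensitivity analyses repeat, has as its covariates "the vaccination group, being at increased risk of RSV disease and age strata (both variables as stratified) as independent variables".

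The sensitivity analyses in Protocol 9.4.1.1 describe no imputation model, and SAP Appendix 2 (changes to protocol-planned analyses) adds none.

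**The concern.** An imputation model should contain the variable whose effect will be estimated from the completed data. Here it does not. Randomisation balances age, risk level and location, so they carry no information about arm. Conditioning on LRTD status does not help either: an effective vaccine removes RSV episodes but not episodes due to other pathogens, so positivity among LRTD-type ARIs still differs by arm.

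What is at stake is interpretation. The section sends its sensitivity analyses to forest plots alongside the primary result. A lower VE on that row could reflect a real effect of missing tests or could be produced by the imputation model. The VE estimate alone does not separate the two.

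**Working it through.** **The plan's own figures.** The documents give no figure for the imputation analysis, so the planning inputs were checked instead. Protocol 9.2.1 gives VE 65%, 2:1 allocation (15,340 and 7,670), placebo incidence of 0.2% then 0.5%, and 10% exclusions per year. Expected placebo events are 7,670 × (0.9 × 0.002 + 0.81 × 0.005) = 44.9. Expected vaccine events are 15,340 × 0.35 × 0.00585 = 31.4. The total is 76.3, against the stated target of 76.

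**Inputs that must be assumed.** m is the share of ARIs with no linked RT-PCR result, taken as 1% to 20%. q is RSV positivity among placebo LRTD-type ARIs, taken as 10% to 90%. Missingness is completely at random, and the non-RSV ARI rate is the same in both arms.

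**Closed form.** Scale the placebo RSV-LRTD rate to 1, so the vaccine rate is 0.35. Events are rare, so the effect on follow-up time is ignored.

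- All LRTD-type ARIs, placebo: a = 1/q
- All LRTD-type ARIs, vaccine: b = 0.35 + (1 − q)/q
- Pooled positivity at 2:1: p = (1 + 2 × 0.35)/(a + 2b)
- Expected VE = 1 − [(1 − m) × 0.35 + m·b·p] / [(1 − m) + m·a·p]

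*Worked case, q = 10%, m = 10%:* a = 10, b = 9.35, p = 1.7/28.7 = 0.0592. The numerator is 0.315 + 0.1 × 9.35 × 0.0592 = 0.3704. The denominator is 0.9 + 0.1 × 10 × 0.0592 = 0.9592. VE = 61.4%.

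| Expected VE (true 65%) | m = 1% | m = 5% | m = 10% | m = 20% |
|---|---|---|---|---|
| q = 10% | 64.65 | 63.23 | 61.39 | 57.45 |
| q = 30% | 64.70 | 63.49 | 61.93 | 58.63 |
| q = 90% | 64.94 | 64.70 | 64.39 | 63.77 |

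Among the untested episodes alone, the implied VE is 1 − b/a = 0.65q: 6.5%, 19.5% and 58.5% at q = 10%, 30% and 90%. At m = 10% over the same range of q, a true VE of 50% becomes 46.8–49.5% and a true VE of 80% becomes 76.3–79.3%.

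**With group in the model.** Vaccine-arm positivity is 0.35/b and placebo positivity is 1/a. The imputed terms become m × b × (0.35/b) = 0.35m and m × a × (1/a) = m. The ratio is then 0.35/1 for any m and q, so VE is 65%.

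**Simulation checks.**

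1. Planned group sizes, an assumed placebo risk of 0.7%, one covariate cell, 20,000 replicates per q × m combination, untested ARIs counted at their estimated positivity. At m = 10%, omitting group gave 61.3, 61.9 and 64.5% for q = 10, 30 and 90%. Including group gave 64.9–65.1% in all 12 combinations, as did leaving untested ARIs uncounted.
2. Logistic multiple imputation with 10 imputations, period and severity as predictors, and groups five times the planned size. Without group, against full data: 62.2 v 64.2 (m = 5%), 61.0 v 64.6 (m = 10%) and 57.6 v 64.8 (m = 20%), all at q = 10%. With group and group × severity, the estimate was within 0.2 points of full data throughout.

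**The case against.** Several points on the other side have force.

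- **No decision rests on it.** Success is defined by the primary exact Poisson lower limit and point estimate. The bias is toward no effect and cannot create a false efficacy claim. This stands and limits the weight of the point.
- **m may be small.** An ARI is imputed only if the home swab, the Day 3-5 swab, any sputum, the central back-up test and any approved hospital test all yield nothing. At m = 1% the shift is under 0.4 points; at m = 5% it is at most 1.8. The 57.5% figure needs both 20% untested and q = 10%, and the documents support neither. This also stands. Period and location may move effective positivity in RSV-season cells toward the small-bias end.
- **Completely random missingness is not the setting that motivates the analysis.** With unequal missingness, the same model at q = 30% and true VE 65% gives the following for placebo/vaccine shares untested: 20%/5%, 58.4% uncounted and 61.4% imputed; 10%/2%, 61.9% and 63.4%; 2%/10%, 67.9% and 62.9%; 5%/20%, 70.5% and 60.5%. So imputation without group can raise VE relative to the primary estimate, and in these cases it lies nearer the truth. That is correct, and the certain direction is relative to true VE only. All four imputed values are still below 65%, whereas imputing with group returns 65% when missingness depends only on arm.
- **It could serve as a conservative stress test.** It could, but the SAP does not present it as one.
- **It may be moot.** SAP 6.11 records that "the Sponsor decided not to perform the complete planned analysis as described in the protocol and SAP", and its list of final analyses does not name this one.

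**Conclusion.** The concern holds. As specified, the imputation model omits the variable whose effect is being estimated, and the result is attenuated relative to true VE whenever VE is above zero, some results are missing and q is below 100%. Over q = 10% to 90% at true VE 65%, the loss is under 0.4 points at m = 1%, 0.3 to 1.8 at m = 5%, 0.6 to 3.6 at m = 10% and 1.2 to 7.5 at m = 20%. These sizes rest on assumed m and q, random missingness and equal non-RSV ARI rates in the two arms. The omission and the direction are firm; the size is not known from the documents. It should be corrected because the analysis does not do what it is meant to do, but the primary test, alpha, power and success criteria are unaffected.

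**What to change.** Add vaccination group as a main effect in the imputation model, with group × LRTD status if it can be fitted, or impute separately by arm. State that group is exempt from the parameters that may be dropped. Report the number of ARIs with no linked RT-PCR result by arm, so that readers can judge the size. If a version without group is kept, label it as a deliberately conservative scenario.

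If the analysis has not been run, amend the SAP text. If it has, rerun it with group and label the rerun post hoc, or report the existing result with this caveat.

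The cost is one model term (optionally one interaction), one SAP sentence and a small table, plus a rerun if the analysis is already done. No new data are needed.
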